5.5. Dose Adjustment/Stopping/Monitoring Criteria

If one or more subject experiences an Serious Adverse Event (SAE) that can be reasonably attributed to GSK2831781, the dose escalation will be halted and no further subject will be dosed until a full safety review of the data has taken place. Relevant reporting and discussion with the DEC, (which must include the GSK medical monitor), relevant GSK personnel, and with the Ethics Committee and Regulatory Agency will then take place. If following the safety review a decision is made to restart dose escalation, this may be allowed after approval of a substantial amendment.

If two or more subjects experience a severe or significant non-serious AE that can be reasonably attributed to GSK2831781, the dose escalation will be halted and no further subject will be dosed until a full safety review of the study has taken place. Relevant reporting and discussion with the DEC (which must include the GSK medical monitor), relevant GSK personnel, and with the Ethics Committee and Regulatory Agency will then take place. If following the safety review a decision is made to restart dose escalation, this may be allowed after approval of a substantial amendment.

Events of note across the cohorts (unless otherwise stated) that will also result in the study being temporarily halted and reviewed by the DEC include:

NOTE: If any of the below occur in the single active subject in the first 2 healthy volunteer cohorts the study will also be reviewed by the DEC.

- 1. Infusion Reaction/Hypersensitivity: Infusion reactions requiring termination of infusion/dosing in 2 or more subjects.
- Cytokine Release Syndrome (CRS): Evidence of CRS leading to moderate clinical symptoms in 2 or more subjects, based on modified NCI-CTC Criteria (see Section 12.3, Appendix 3). Symptoms include: Headache, fever, chills/rigors, nausea, vomiting, diarrhoea, arthalgia, myalgia, hypotension.
- 3. Neutropenia (the following must be confirmed by repeat samples):
 - If one subject experiences neutrophil count $<1.5 \times 10^9/L$ for >7 days for the first 28 days for the first 2 healthy volunteer cohorts.
 - If one or more subjects experiences neutrophil count $<0.5 \times 10^9$ /L for >7 days
 - If 2 or more subjects experience neutrophil count $<0.5 \times 10^9$ /L for <7 days.
 - If 2 or more subjects experience clinically significant neutropenia for >7 days.

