5.6.6. Other Dose Adjustment/Stopping Safety Criteria

Symptoms of hypersensitivity which require stopping of infusion, together with appropriate management are described in Section 6.3.4.

The reason(s) for discontinuation of the study treatment must be recorded in the subject's electronic case report form (CRF). Subjects whose infusion is terminated prematurely will be expected to complete the remainder of the study visits so that study data are collected.

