6.3.4. Infusion-related Reactions and Hypersensitivity Reactions

Subjects with a history of allergies or urticaria, allergic responses to foods, drugs, or insects may receive diphenhydramine and paracetamol (acetaminophen) prior to dosing at the discretion of the Principal Investigator or as a result of emerging data. Subjects will be closely monitored for signs of infusion-related reactions and acute allergic reactions and/or anaphylaxis following the administration of GSK2831781. If an infusion-related reaction occurs during administration, the infusion rate will be reduced or halted. The subject will receive appropriate medical treatment. When the subject's condition is stable, the infusion may be restarted and the infusion rate will be half of the infusion rate at the time the infusion was paused. Severe hypersensitivity reactions such as anaphylaxis, will result in immediate termination of the infusion and the infusion will not be restarted.

As GSK2831781 is a fully humanized monoclonal antibody, it is considered unlikely for acute allergic reactions to occur in response to GSK2831781 exposure; however, all subjects will be monitored carefully for evidence of allergic response. A subject that exhibits signs or symptoms of severe hypersensitivity or anaphylaxis will receive appropriate medical treatment and remain on study at the discretion of the investigator and after discussion with the GSK medical monitor. In the event of a suspected acute hypersensitivity reaction a blood sample should be taken between 30 minutes – 3 hours of the event for serum tryptase analysis.

In accordance with the preparedness for treatment of anaphylaxis, emergency resuscitation equipment, advanced cardiac life support equipment, and medications must be readily accessible during GSK2831781 administration.

If more severe clinical signs arise, immediate assessment of the ABC's (airway, breathing, and circulation from Basic Life Support) will be done in all suspected anaphylactic reactions. Cardio-Pulmonary Resuscitation (CPR) will be initiated if needed. Epinephrine will be given by injection without delay. Emergency interventions may include endotracheal intubation or tracheostomy. Treatment for shock will include IV fluids and medications that support the actions of the heart and circulatory system.

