14.9.13. ICH Listings

ICH: Lis	CH: Listings							
No.	Population	IDSL / Example Shell	Title	Programming Notes	Deliverable			
1.	Safety	DM2	Listing of demographic characteristics for healthy volunteers		IA1			
2.	Safety	DM2	Listing of demographic characteristics for psoriasis patients		IA2 W2			
3.	Safety	AE7	Listings of subject numbers for individual adverse events for healthy volunteers		SAC			
4.	Safety	AE7	Listings of subject numbers for individual adverse events for psoriasis patients	same as for HV	IA2 W2			
5.	Safety	CP_AE8	Listing of all adverse events for healthy volunteers		IA2 W2			
6.	Safety	CP_AE8	Listing of all adverse events for psoriasis patients	same as for HV	IA2 W2			
7.	Safety	CP_AE8a	Listing of serious adverse events for healthy volunteers	Same as for all Aes	IA2 W2			
8.	Safety	CP_AE8a	Listing of serious adverse events for psoriasis patients	same as for HV	IA2 W2			
9.	Safety	CP_AE8	Listing of adverse events leading to withdrawal from study for healthy volunteers		SAC			
10.	Safety	CP_AE8	Listing of adverse events leading to withdrawal from study for psoriasis patients		SAC			
11.	Safety	CP_LB5	Listing of clinical chemistry abnormalities of potential clinical importance for healthy volunteers		IA2 W2			
12.	Safety	CP_LB5	Listing of clinical chemistry abnormalities of potential clinical importance for psoriasis patients		IA2 W2			
13.	Safety	CP_LB6	Listing of all clinical chemistry laboratory data for subjects with PCI abnormalities for healthy volunteers		IA1 SAC			

ICH: Lis	ICH: Listings					
No.	Population	IDSL / Example Shell	Title	Programming Notes	Deliverable	
14.	Safety	CP_LB6	Listing of all clinical chemistry laboratory data for subjects with PCI abnormalities for psoriasis patients		IA2 W2	
15.	Safety	CP_LB5	Listing of haematology abnormalities of potential clinical importance for healthy volunteers		IA2 W2	
16.	Safety	CP_LB5	Listing of haematology abnormalities of potential clinical importance for psoriasis patients		IA2 W2	
17.	Safety	CP_LB6	Listing of all haematology laboratory data for subjects with PCI abnormalities for healthy volunteers		SAC	
18.	Safety	CP_LB6	Listing of all haematology laboratory data for subjects with PCI abnormalities for psoriasis patients		IA2 W2	
19.	Safety	UR2a	Listing of urinalysis data for healthy volunteers		IA1 SAC	
20.	Safety	UR2a	Listing of urinalysis data for psoriasis patients		SAC	
21.	Safety		Listing of CMV and EBV serology for healthy volunteers		SAC	

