22.	Safety		Listing of CMV and EBV serology for psoriasis patients		SAC	
23.	Safety	CP_EG3	Listing of ECG values of potential clinical importance for healthy volunteers		IA2 W2	
24.	Safety	CP_EG3	Listing of ECG values of potential clinical importance for psoriasis patients		IA2 W2	
25.	Safety	CP_EG3	Listing of all ECG values for subjects with any value of potential clinical importance for healthy volunteers		IA2 W2	
26.	Safety	CP_EG3	Listing of all ECG values for subjects with any value of potential clinical importance for psoriasis patients		IA2 W2	
27.	Safety	CP_EG5	Listing of abnormal ECG findings for psoriasis patients		IA2 W2	

ICH: Li	ICH: Listings					
No.	Population	IDSL / Example Shell	Title	Programming Notes	Deliverable	
28.	Safety	CP_VS4	Listing of vital signs of potential clinical importance for healthy volunteers		IA2 W2	
29.	Safety	CP_VS4	Listing of vital signs of potential clinical importance for psoriasis patients		IA2 W2	
30.	Safety	CP_VS4	Listing of all vital signs for subjects with any value of potential clinical importance for healthy volunteers		IA1 SAC	
31.	Safety	CP_VS4	Listing of all vital signs for subjects with any value of potential clinical importance for psoriasis patients		SAC	
64	Safety	CP_TA1	Listing of randomised and actual treatments for healthy volunteers		SAC	
65	Safety	CP_TA1	Listing of randomised and actual treatments for psoriasis patients		SAC	
66	Safety	ES2	Listing of reasons for study withdrawal for healthy volunteers		SAC	
67	Safety	ES2	Listing of reasons for study withdrawal for psoriasis patients		SAC	
68	All screened	ES7	Listing of reasons for screening failure for healthy volunteers		SAC	
69	All screened	ES7	Listing of reasons for screening failure for psoriasis patients		SAC	
70	Safety	DV2	Listing of important protocol deviations for healthy volunteers		SAC	
71	Safety	DV2	Listing of important protocol deviations for psoriasis patients		SAC	

ICH: Li	ICH: Listings					
No.	Population	IDSL / Example Shell	Title	Programming Notes	Deliverable	
72	Safety		Listing of Subjects with Inclusion/Exclusion Criteria Deviations for Healthy Volunteers		SAC	
73	Safety		Listing of Subjects with Inclusion/Exclusion Criteria Deviations for Psoarisis Patients		SAC	
74	Safety		Listing of Race for Healthy Volunteers		SAC	
75	Safety		Listing of Race for Psoarisis Patients		SAC	
76	Safety	SA3a	Listing of subjects excluded from any population for healthy volunteers		SAC	

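### No planned adverse event display picks out or counts events that ended the infusion: SAP Listings 9 and 10 select on leaving the study, which a stopped infusion is not expected to cause

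*SAP*

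**What the plan says.** SAP section 14.9.13 plans "Listing of adverse events leading to withdrawal from study for healthy volunteers" (Listing 9) and "Listing of adverse events leading to withdrawal from study for psoriasis patients" (Listing 10). The disposition listings use the same key: Listing 67 is "Listing of reasons for study withdrawal for psoriasis patients", and Listing 66 is its healthy volunteer counterpart.

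The protocol separates stopping treatment from leaving the study. Section 5.6.6 states: "Subjects whose infusion is terminated prematurely will be expected to complete the remainder of the study visits so that study data are collected". The same section requires the reason for discontinuing treatment to be recorded in the eCRF. Section 6.3.4 foresees the event: "Severe hypersensitivity reactions such as anaphylaxis, will result in immediate termination of the infusion and the infusion will not be restarted". It adds that such a subject may "remain on study at the discretion of the investigator and after discussion with the GSK medical monitor". Section 5.5 counts these events for study conduct. Among the events that also halt the study pending committee review is "Infusion reactions requiring termination of infusion/dosing in 2 or more subjects".

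**The concern.** With one infusion per subject, treatment can be discontinued after dosing starts only by stopping that infusion. A listing of AEs leading to discontinuation should capture that event. Listings 9 and 10 select instead on an outcome that protocol 5.6.6 does not expect to follow it.

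Tolerability of a single IV dose is part of the primary objective. A reader of the clinical study report who finds no entry in the withdrawal listings may conclude that every infusion was tolerated to completion. The plan would not support that conclusion. The reason for stopping is collected and a halting rule depends on a closely related count, yet no planned display reports that count.

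**Working it through.** No sample size or power figure bears on this point. The check compares the displays in SAP Appendix 9 with the protocol rules on stopped infusions.

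**Step 1: what happens to the subject.** Under protocol 5.6.6, a subject whose infusion is stopped is expected to stay to the end of the visits. Under 6.3.4, staying after severe hypersensitivity is possible at the investigator's discretion. The default is therefore that the subject is not a study withdrawal.

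**Step 2: where the AE appears.** SAP 14.2.2 treats any AE starting between first dose and the last scheduled visit as treatment-emergent. A reaction during the infusion therefore enters:
- Tables 3.1 and 3.2 (all AEs), and 3.3 and 3.4 if drug-related;
- Tables 3.10 and 3.11 if serious;
- Listings 5 and 6 (all AEs), and 7 and 8 if serious.

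**Step 3: whether any display identifies it as dose-terminating.** Going by titles and programming notes:
- AE tables: 3.1 to 3.11 plus 3.36 and 3.37, so 11 + 2 = 13. None is keyed to stopping treatment.
- AE listings: 3 to 10, so 8. Two (9 and 10) are keyed to study withdrawal and none to stopping treatment.
- Listings 66 and 67 give reasons for study withdrawal.
- Listings 64 and 65 give randomised and actual treatment. SAP 14.3.1.2 copies actual treatment from assigned treatment unless the wrong treatment was taken, and allows a separate code for untreated subjects. A partial infusion changes neither.
- Listings 70 and 71 give important protocol deviations. Stopping an infusion for a reaction follows protocol 6.3.4, so it need not be a deviation.
- SAP 7.1 mentions other significant AEs but refers to Appendix 9 for the displays, and none there fills the gap.

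**Step 4: size.** If k infusions in a cohort are stopped for AEs and all k subjects stay, Listings 9 and 10 show 0 of the k events for any k. A psoriasis cohort has 6 active subjects. With k = 2, 2/6 = 33% of active subjects would have had dosing ended, two subjects being the number named in the infusion-reaction criterion of protocol 5.5. Listing 10 would show neither event.

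**The case against.** The strongest reply is that nothing is hidden. Every such AE is tabulated by system organ class and preferred term and appears in the full AE listings. With about 67 subjects and at most 6 active per cohort, a reader can go through those listings line by line. That is right about the events themselves. What is missing is the selection and the count.

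The mock shells are available only on request and AE reporting follows sponsor standards that are not in the documents, so Listings 5 and 6 may carry a column for action taken. That would identify the event for someone who searches for it. It would still give neither a dedicated listing nor a count by treatment group.

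The protocol says only that subjects are expected to stay, and staying after severe hypersensitivity is discretionary. Listings 9 and 10 could therefore capture some stopped infusions. That stands, and the zero result is conditional on subjects staying.

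A reader might also infer more than the documents support:
- **That subject safety is exposed.** The dose escalation committee reviews safety during conduct. Infusion reaction is item 1 of a list that follows two general halting rules in protocol 5.5, one for attributable SAEs and one for severe or significant non-serious AEs. The final listings play no part in these decisions.
- **That partial doses go unmarked in every display.** The shells are not shown, so this cannot be established.
- **That clearance would be biased, for example doubled for an infusion stopped halfway.** This would require the nominal dose in dose divided by AUC. SAP 9.2 does not say which dose is used, and the guidance cited in SAP section 9 is not in the documents.

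**Conclusion.** The point holds as a reporting gap. The only AE displays tied to discontinuation select on study withdrawal, while the protocol expects subjects with a terminated infusion to remain. AEs that end dosing are counted and listed among all AEs, but no planned display is keyed to them or counts them as dose-terminating. If subjects stay as expected, Listings 9 and 10 show none of them, whatever their number.

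This rests on two assumptions: that sites follow protocol 5.6.6, and that titles and programming notes describe the displays fully. It does not depend on any infusion actually having been stopped. The gap should be closed because it touches the primary objective, the reason for stopping is already collected, and the change is small.

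**What to change.** 1. Extend Listings 9 and 10, or add a paired listing for each population, to cover AEs leading either to permanent discontinuation of study treatment or to study withdrawal. Include a column showing which applies, so the two outcomes are not mixed.
2. Add one row to Tables 3.1 and 3.2 giving, by treatment group, the number of subjects with an AE that led to discontinuation of study treatment. Print the row even when the count is zero.
3. Flag subjects with a terminated infusion in the PK listings (32 to 35), using the discontinuation reason in the eCRF.

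The cost is SAP wording, one changed filter, one added row and a flag. It needs no change to dosing rules, visits or data collection.

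A listing of infusion stop times and dose received should be added only if those data are confirmed to be in the eCRF. Protocol 5.11 places the date and time of dosing in source documents, and the documents do not show that stop times, interruptions or delivered volume reach the eCRF.

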14.9.14. Non-ICH Listings

Non-ICH: Listings					
No.	Population	IDSL / Example Shell	Title	Programming Notes	Deliverable
32.	PK	PK07	Listing of plasma GSK2831781 pharmacokinetic concentration-time data for healthy volunteers		IA2 W2
33.	PK	PK07	Listing of plasma GSK2831781 pharmacokinetic concentration-time data for psoriasis patients		IA2 W2
34.	PK	PK13	Listing of derived plasma GSK2831781 pharmacokinetic parameters for healthy volunteers		IA2 W2
35.	PK	PK13	Listing of derived plasma GSK2831781 pharmacokinetic parameters for psoriasis patients		IA2 W2
36.	Safety	IMM2	Listing of immunogenicity results for healthy volunteers	NAB assay results included for SAC	IA2 W2
37.	Safety	IMM2	Listing of immunogenicity results for psoriasis patients	same as for HV	IA2 W2
38.	Safety		Listing of induration diameter for healthy volunteers (DTH subjects)		IA1
39.	Safety		Listing of duration of induration for healthy volunteers (DTH subjects)		IA1
40.	safety		Raw sas output statistical analysis results of change from baseline in induration diameter for healthy volunteers (DTH subjects)		IA1
41.	safety		Raw sas output statistical analysis results of duration of induration for healthy volunteers (DTH subjects)		IA1
42.	Safety	LS1	Listing of PASI-related endpoints for psoriasis patientss		SAC
43.	Safety		Listing of PASI components for psoriasis patients		SAC

Non-IC	Non-ICH: Listings					
No.	Population	IDSL / Example Shell	Title	Programming Notes	Deliverable	
44.	Safety		Listing of BSA scores for psoriasis patients		SAC	
45.	Safety		Raw sas output of statistical analysis results for change from baseline in PASI scores for psoriasis patients		IA2 EFF IA2	
46.	Safety		Raw sas output of statistical analysis results for change from baseline in PLSS score for psoriasis patients		IA2 EFF IA2	
47.	Safety		Listing of PLSS-related endpoints for psoriasis patients		SAC	
48.	Safety		Listing of PGA-related endpoints for psoriasis patients		SAC	
49.	Safety		Listing of cytokines for healthy volunteers		IA1	
50.	Safety		Listing of cytokines for psoriasis patients		SAC	
51.	Safety		Listing of flow cytometry for healthy volunteers	All the parameters, not only the 6 key ones	IA1	
52.	Safety		Listing of flow cytometry for psoriasis patients	All the parameters, not only the 6 key ones	SAC	
53.	Safety		Listing of LAG3+ and CD3+ in skin for healthy volunteers (DTH subjects)		IA1	
54.	Safety		Listing of cells in lesional biopsies measured by IHC for psoriasis patients		SAC	
55.	Safety		Listing of epidermis thickness for psoriasis patients		SAC	
56.	Safety		Raw sas output of statistical analysis results for change from baseline LAG3+ and CD3+ for healthy volunteers (DTH subjects)		SAC	

Non-ICH: Listings					
No.	Population	IDSL / Example Shell	Title	Programming Notes	Deliverable
57.	Safety		Raw sas output of statistical analysis results for change from baseline in cells in lesional biopsies measured by IHC for psoriasis patients		SAC
58.	Safety		Raw sas output of statistical analysis results for change from baseline in epidermis thickness for psoriasis patients		SAC
59.	Safety		Listing of sLAG-3 for healthy volunteers		SAC
60.	Safety		Listing of sLAG-3 for psoriasis patients		SAC
61.	Safety		Listing of blood transcriptomics for healthy volunteers	Includes raw Ct as well as average (mean delta Ct, delta delta Ct and fold change)	SAC
62.	Safety		Listing of blood transcriptomics for psoriasis patients		SAC
63.	Safety		Listing of biopsy transcriptomics for psoriasis patients		IA2 W2
8 1	Safety	other	Listing of PPD challenge for healthy volunteers (DTH subjects)		SAC

14.10. Appendix 10: Example Mock Shells for Data Displays

Data Display Specification will be made available on Request.
